## 6.3 Antidrug Antibody

Anti-drug antibody (ADA) sampling will be performed at the time points shown in Appendix 1 Table 1 (Part A), Table 2 (Part B, Cohort 4) and Table 3 (Part B, Cohort 5). ADA-positive or ADA-negative will be determined for each time point. If the first test comes back positive then the reactivity to the pgal and peptide will be assessed separately. Titers will be determined for ADA positive sample if the quantity is sufficient for the determination.

6.4	

#### 6.5 Other Assessments

Additional assessments will be collected for demographics, medical history, concomitant medication, informed consent inclusion/exclusion, study drug administration will be explained in more detail in Section 8.

#### 7. ANALYSIS SETS

**Enrolled Analysis Set** is defined as all patients in Part A and Part B who were enrolled in the study and signed informed consent form.

**All-Treated Analysis Set (ATAS)** is defined as all patients who receive any amount of study drug. This analysis set will be the primary analysis set for all safety and exploratory endpoints.

**PK Analysis Set (PKAS)** will include all enrolled patients who receive  $\geq 1$  complete dose of study drug and have  $\geq 1$  pre-dose and 1 post-dose measurement. This analysis set will be used for the analysis of PK parameters as further defined in the protocol.

Patients who receive at least one full dose out of the three doses will be included in this population; if a patient misses a dose or does not complete a dose then the PK concentration data, for that observation, will be considered missing.

## 8. STATISTICAL METHODS

All outputs will be produced using SAS® version 9.4 or a later version.

No hypothesis will be tested.

Summary statistics will be presented for all variables of interest for the ATAS population unless otherwise specified. Categorical variables will be summarized using numbers and percentages and be presented by dose level received. Continuous variables will be summarized by total number (n), mean, standard deviation (SD), median, and range (minimum and maximum). For log transformed data, the geometric mean will be provided along with the other summary statistics. Categorical data will be presented by frequency and percent of patients in the treatment group.

Listings will be sorted by Study Part, subject ID, Treatment, study visit, date and time, where applicable, unless otherwise specified.

Summary statistics for Part A and B will be presented in the following manner:

- For Part A, summary statistics will be provided for subject disposition with the following tables summarized:
  - o Disposition
  - Analysis populations
  - Demographics
  - Protocol Deviations
  - PK analysis
  - Summary of TEAE
  - o Summary of TEAE by System Organ Class and Preferred Term
- For Part B alone, summary statistics will be provided by treatment group, pooling the placebo group from each cohort for all tables.
- For Part A and B pooled, summary statistics will be provided by pooling the treatment groups with only the following tables summarized:
  - o Disposition
  - Analysis Populations
  - Demographics
  - o PK analysis

## 8.1 Data Quality Assurance

All tables, figures and data listings to be included in the report will be independently checked for consistency, integrity and in accordance with standard Parexel procedures.

#### 8.2 Subject Disposition and Screen Failures

The number and percentage of patients in each disposition category (eg, enrolled, analysis sets, discontinuing treatment, and discontinuing study, with a breakdown of the reasons for discontinuation) will be summarized by treatment group for all patients.

A clear accounting of the disposition of all patients who enter the study will be provided, from screening to end of study participation. Number and percentage of patients screened, enrolled/randomized, patients completed treatment, patients discontinued from the study and discontinuation reasons (including reasons for early withdrawal).

The summary tables will be provided by treatment group for subject disposition on enrolled patients. Listing will consist of ICF date, enrollment details (last contact date, reason of

screened failure), randomization codes, visit dates, and withdrawal details (including reason for discontinuation and duration of treatment prior to discontinuation).

A by-subject listing will be provided by study part and treatment group for study treatment/randomization codes, study drug completion status, study completion status and subject disposition on enrolled patients. Screen failures, and patients who did not meet study eligibility criteria listings will be on listing of screened patients.

#### **8.3** Prior and Concomitant Medication

Medication start and stop dates will be compared to the date of first dose of ANK-700 to allow medications to be classified as either Prior only, both Prior and Concomitant, or Concomitant only. Medications starting after the completion/withdrawal date will be listed but will not be classified or summarized.

Medications will be assigned to a time period (prior and /or concomitant) as follows:

- If medications that start and stop prior to the date of first dose of ANK-700, the medications will be classified as Prior only.
- If the start date is missing and the stop date is before the first dose of study drug, the medication will be counted as prior.
- If a medication starts before the date of first dose of ANK-700 and stops on or after the date of first dose of ANK-700, then the medication will be classified as both Prior and Concomitant
- If the start date is missing and the stop date is after the first dose of study drug or the medication is continuing, the medication will be counted as concomitant only.
- If they have a start date on or after the date of first dose of ANK-700, medications will be classified as Concomitant only.
- If medication start and/or stop dates are missing or partial, the dates will be compared as far as possible with the date of first dose of ANK-700.

All concomitant medication and concurrent therapies as documented by the investigator, will be coded using the most current version of the WHO drug dictionary (WHO DD) available at the time of database lock.

If a patient has taken concomitant medications more than once, the patient will be counted only once in the total. The number and percentage of patients taking prior and concomitant medications will be summarized by WHO Drug Name.

For Part A and B, summary tables (as described in Section 7) will be provided by treatment group for prior and concomitant medications by ATC Levels and PT.

By-subject listings of concomitant medication and concurrent therapies including dose, route, unit frequency of administration, and indication for administration and dates of medication will be provided on enrolled patients and sorted by part, subject ID and date of medication start.

After patients have completed the 3-month visit (D90), they may receive alternative DMTs (Disease modifying Therapy) for their MS if judged clinically appropriate by their treating physician or the Investigator. Summary statistics for observations after 90 days may be presented in a sample size report, stratified by medication, if sample size permits.

#### 8.4 Demographics, Baseline Characteristics, Disease History and Medical History

Patient listings will be presented for all enrolled patients for Part A and Part B, by treatment group, center, and subject ID for enrolled patients unless otherwise specified. Listings will be sorted by part and subject id unless otherwise specified.

Demographics and baseline characteristics will be summarized by treatment (PBO and dose group) for the All-Treated Analysis Set: sex, race, age, ethnicity, height, weight, BMI.

All medical history will be coded using Version 23.1 or higher of the Medical Dictionary for Regulatory Activities (MedDRA). A count and percentage will be presented for all medical history, including disease history and previous therapies. MS history is considered part of medical history and the following will be summarized (as stated in Section 7): concomitant fumarate use, duration since MS symptom onset, duration since MS diagnosis, number of relapses within the last year, number of relapses within the past 3 years, duration since last relapse, and use of previous MS treatments.

## 8.5 Study Drug Administration and Compliance

A by-subject listing for study drug administration and compliance will be provided by study part and treatment group on enrolled patients

The treatment compliance (%) at a study part and treatment group will be calculated as total received dose (mg) \*100/sum of total intended dose (mg) during the treatment.

#### 8.6 Dosing and Extent of Exposure

Exposure will be calculated for study Part A and Part B by dose level; all exposure data will be listed (for details see Section 7) for both parts. The exposure variables include:

- the cumulative number of days of exposure- count of days of treatment
- the number of IV infusions completed
- the relative dose intensity

## All variables are predefined:

• The relative dose intensity is defined as the percentage of the planned treatments completed. It is the ratio of the cumulative actual dose (mg) and cumulative planned dose (mg) times 100. In this definition,

- o the cumulative actual dose (mg) is the sum of the actual doses (mg) that the patient receives during the study
- o the cumulative planned dose (mg) is the cumulative number of days of exposure times the planned dose level (mg)

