#### 4.9. INDIVIDUAL AND COHORT STOPPING RULES

During the dose-escalation safety monitoring period, any DLT will result in a pause in enrollment and a thorough review by the SMC before treating any additional patients. Any ≥ Grade 4 AE will result in notification of the FDA in parallel with the SMC, and study dosing and enrollment will be paused pending review by FDA.

For Part A, if 1 of the first 3 patients experiences a DLT within the safety monitoring period (D1 to D15) in a given cohort, 3 additional patients will be enrolled and evaluated in that cohort before dose escalation can occur if recommended by the SMC and only after consultation with the FDA for any  $\geq$  Grade 4 AE. If 2 or more patients experience a DLT at a given dose level during the dose escalation evaluation period of Part A (D1 to D15), then that dose level will be considered to have exceeded the non-tolerated dose (NTD), and no further escalation will proceed.

If a patient experiences a DLT during the dose-escalation safety monitoring period of Part B, no additional doses will be administered to that patient. If 1 patient experiences a DLT during the dose-escalation safety monitoring period of Part B, the study will be paused to determine if any dose adjustments are needed and/or if the study should dose any additional patients. For any  $\geq$  Grade 4 AE, the study will only continue after consultation with the FDA. If 2 or more patients experience a DLT during the dose-escalation safety monitoring period of Part B (D1 to D22), then that dose level will be considered to have exceeded the NTD, and no further escalation will proceed.

The maximum tolerated dose (MTD) will be defined as the proximal dose level below the dose exceeding the NTD administered during the study. Of note, dose escalation may not identify an NTD or MTD.

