### **12.4. ANK-700 EXPOSURE**

Exposure will be calculated for study Part A and Part B by dose level; all exposure data will be listed for both parts. The exposure variables include:

- the cumulative number of days of exposure
- the number of IV infusions completed
- the relative dose intensity

All variables are predefined:

- The relative dose intensity is defined as the percentage of the planned treatments completed. It is the ratio of the cumulative actual dose (mg) and cumulative planned dose (mg), multiplied by 100. In this definition,
  - the cumulative actual dose (mg) is the sum of the actual doses (mg) that the patient receives during the study
  - the cumulative planned dose (mg) is the cumulative number of days of exposure multiplied by the planned dose level (mg)

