## 2.3.2 PART B: MAD (Multiple Ascending Doses)

The first MAD cohort (Cohort 4) will be initiated after the safety review of SAD Cohort 2 (Part A), a recommendation to proceed by the SMC, and approval by the Sponsor.

Patients in the MAD part will be randomized as described in Section 3.2. Patients will arrive at the clinic on the morning of dosing and will be monitored in-clinic for 24 hours after completion of their first infusion for assessment of acute safety and PK blood sample collection.

A total of 3 doses (1 dose every 3 days on D1, D4, and D7) will be administered in Part B, a regimen that was effective in animal models of MS. Patients will return to the clinic on D22, D43±2, and at 3, 6, and 12 months for follow-up.

Doses planned for evaluation in Part B include 0.3 mg/kg (Cohort 4) and 1.0 mg/kg (Cohort 5). Both Part B cohorts will employ sentinel dosing to monitor for the acute and subacute safety of multiple doses of ANK-700. In this design, the first 2 patients in each cohort (1 ANK-700 and 1 PBO) will complete all 3 doses and complete an additional 14 days of safety monitoring (through D21) before initiating dosing for any subsequent patients. Based upon the expected short half-life (< 7 minutes) of ANK-700, no accumulation is anticipated with multiple doses administered 3 days apart.

Initiation of Cohort 5 will only commence after review of the safety, tolerability, and laboratory test and available PK data of all the SAD cohorts (Cohorts 1 to 3) and Cohort 4 through D22, recommendation by the SMC, and approval by the Sponsor.

For all patients in Part B, the study will consist of a screening period of up to 28 days, followed by 3 doses of study drug, 1 dose administered on D1, D4, and D7. Blood and plasma samples will be collected for PK and ADA assessments during Part B of the study. In

the event that patients are unable to return to the clinic for protocol-specified visits, alternative methods for safety assessments and data collection may be employed to ensure the safety of the patients where appropriate.

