#### 3. SAMPLE SIZE, RANDOMIZATION AND BLINDING

## 3.1 Sample Size

In Part A, the number of patients enrolled into a treatment group will be based on safety and tolerability within a traditional 3+3 design. If 1 of the first 3 patients in a given cohort experiences a DLT within the dose-escalation safety monitoring period (D1 to D15), the dose level may expand to a maximum of 6 patients under this model, Part A may enroll 9 to 18 patients across 3 treatment groups, depending upon the toxicities observed. No formal hypothesis testing is planned for Part A.

Patients in Part A may be replaced if they do not receive the full dose of study drug or do not complete the D15 visit, as long as the discontinuation was not due to a DLT assessed to be related to study drug.

In Part B, the total sample size of 24 patients (n=8 ANK-700 0.3 mg/kg; n=8 ANK-700 1 mg/kg; n=8 PBO) was chosen to allow for a comparison of safety between ANK-700 and PBO, however no sample size calculation was performed.

In Part B, patients may be replaced if they do not complete all 3 doses and the D22 visit as long as they did not discontinue the study because of a related AE. No patient with a DLT will be replaced.

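### In Part B, relative dose intensity ignores infusions that were never given, so a patient with 1 or 2 full infusions of the 3 planned scores 100%

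*SAP*

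**What the plan says.** SAP 8.6 lists three exposure variables: days of exposure, number of infusions completed, and relative dose intensity (RDI). It explains the last in words: "The relative dose intensity is defined as the percentage of the planned treatments completed". It then gives a formula, 100 times the cumulative actual dose over the cumulative planned dose, both in mg. The denominator is defined as follows: "the cumulative planned dose (mg) is the cumulative number of days of exposure times the planned dose level (mg"). Days of exposure are themselves defined as "the cumulative number of days of exposure- count of days of treatment".

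Protocol 12.4 has the same denominator: "the cumulative planned dose (mg) is the cumulative number of days of exposure multiplied by the planned dose level (mg").

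The planned course in Part B is fixed. SAP 2.3.2 states: "A total of 3 doses (1 dose every 3 days on D1, D4, and D7) will be administered in Part B". In Part A it is a single infusion.

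The documents also provide for patients who do not finish the Part B course. SAP 3.1 says: "In Part B, patients may be replaced if they do not complete all 3 doses and the D22 visit", subject to a condition on the reason for stopping. Protocol 4.9 says that after a Part B DLT "no additional doses will be administered to that patient". Such patients stay in the All-Treated Analysis Set, which SAP 7 defines as "all patients who receive any amount of study drug".

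**The concern.** A day without an infusion is not a day of treatment. An infusion that is missed entirely therefore adds nothing to the actual dose and nothing to the planned dose, and the ratio does not change. Only an infusion that was started and not finished can lower RDI. The formula thus measures how completely the started infusions were delivered. The sentence above it promises the share of the planned course that was delivered.

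The patients affected are those for whom an exposure measure is most informative in a tolerability study: those who stop dosing early, including after a DLT. An exposure table could show an arm at full dose intensity although some of its patients received one infusion of three.

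**Working it through.** **Inputs**

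- Planned infusions: 3 in Part B (D1, D4, D7; SAP 2.3.2) and 1 in Part A (SAP 2.4).
- Days of exposure: the count of treatment days (SAP 8.6).
- ANK-700 patients per Part B cohort: 8 (SAP 3.1).
- The documents give no numerical RDI, so there is no stated figure to reproduce.

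**Formulas.** Let *d* be the planned mg per infusion, *f* the fraction of an infusion given, and *n* the number of days on which an infusion was started.

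- SAP 8.6: RDI = 100 × (*d* × Σ*f*) / (*n* × *d*) = 100 × Σ*f* / *n*
- Planned course, Part B: RDI = 100 × (*d* × Σ*f*) / (3 × *d*) = 100 × Σ*f* / 3

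The dose *d* cancels, so the results are the same at 0.3 and 1.0 mg/kg and at any body weight.

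| Infusions received in Part B | SAP 8.6 | Planned course |
|---|---|---|
| 3 full | 3/3 = 100% | 3/3 = 100% |
| 2 full | 2/2 = 100% | 2/3 = 66.7% |
| 1 full | 1/1 = 100% | 1/3 = 33.3% |
| 2 full, then half of the third | 2.5/3 = 83.3% | 2.5/3 = 83.3% |
| 1 full, half of the second, stop | 1.5/2 = 75% | 1.5/3 = 50% |
| Half of the first, stop | 0.5/1 = 50% | 0.5/3 = 16.7% |

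The two formulas agree when all three infusions are started and diverge when one is missed. Comparing the third and fourth rows shows the reversed ranking: 100% for one infusion of three, 83.3% for two and a half of three.

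**Does another reading of days of exposure help?** If it meant elapsed days from D1 to the last infusion, a fully dosed patient would score 3/7 = 42.9%, D1 and D4 only would score 2/4 = 50%, and D1 only would score 1/1 = 100%. A complete course would then score below 100%, so this reading is unworkable. The SAP's own definition also points away from it.

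**Effect on an arm mean.** Take 8 patients, seven of them fully dosed.

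- The eighth stops after one full infusion: (7 × 100 + 33.3)/8 = 91.7%, a fall of 8.3 points.
- The eighth stops after two full infusions: (7 × 100 + 66.7)/8 = 95.8%, a fall of 4.2 points.
- SAP formula in both cases: (8 × 100)/8 = 100%, a fall of 0.

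If the early stopper is replaced and both patients stay in the All-Treated set, the arm has 9 patients and the falls become 66.7/9 = 7.4 and 33.3/9 = 3.7 points.

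**Part A.** With one planned infusion, *n* = 1 for every treated patient and the two formulas coincide.

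**The case against.** The arithmetic is hard to contest; the stronger case is that it matters little.

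- **Other outputs show early stops.** The number of infusions completed is in the same list in SAP 8.6, all exposure data are listed, and SAP 8.2 and 8.8.1 report discontinuations and their reasons. This stands and limits the harm. It does not make the formula correct, since those outputs would visibly disagree with an RDI of 100%.
- **SAP 8.5 compliance may already be the planned-course measure.** It divides the dose received by the dose intended during treatment. The text does not say whether infusions after discontinuation count as intended, so it is not a clear safeguard.
- **The verbal definition and the formula conflict, so the output is not settled.** The conflict is real. The formula is the operational part and is labelled predefined, so it is what a programmer would most likely implement.
- **Missed infusions may be few.** The documents give no rate. The DLT route is also narrow: dosing ends on D7, and a Grade 2 event must fail to resolve for 14 days before it counts, so only a Grade 3 or higher event before the third infusion can remove an infusion by that route. This stands as a point about frequency. Protocol 4.10 and 10.5 give further routes to stopping.
- **The mean is inferred.** SAP 8.6 says only that exposure is calculated by dose level and listed. A tabulated mean follows from the general text of SAP 8. The patient-level errors do not depend on it.
- **Planned mg is zero for placebo patients.** This is true, but it applies equally to the current formula.

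**Conclusion.** The concern holds. As written, the Part B formula does not yield the quantity that SAP 8.6 says it defines. It gives 100% where the planned-course value is 33.3% (one full infusion) or 66.7% (two), and it can order patients wrongly. At arm level it hides a fall of 8.3 or 4.2 points per early stopper. Those figures assume an arm of 8 including that patient, the others fully dosed, and a mean being tabulated; with one replacement they are 7.4 and 3.7.

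The conclusion rests on the SAP's own definition of days of exposure as a count of treatment days. The consequence is confined to one descriptive exposure variable in Part B. The primary endpoint and the DLT assessment do not use it. It should be corrected before database lock because the error is certain whenever an infusion is missed and the correction is cheap.

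**What to change.** In SAP 8.6, define the cumulative planned dose as the number of infusions planned by the protocol (1 in Part A, 3 in Part B) times the planned dose in mg per infusion (assigned mg/kg times dosing weight), whether or not the infusions were given. For placebo patients, state the convention used, for example the fraction of planned infusions delivered, since an ANK-700 dose in mg is not defined for them.

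In SAP 8.5, state whether the intended dose covers the full planned course. If it does, compliance and the corrected RDI are the same quantity and one can be dropped.

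Protocol 12.4 should carry the same definition. Protocol 12 lets the final SAP prevail, so the SAP change is sufficient for the analysis if the protocol is not otherwise being amended.

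The cost is one sentence in SAP 8.6, one clarification in SAP 8.5, a placebo convention and one derived variable, with no new data. The downsides are a lower figure for patients who stop early and possible redundancy with the compliance percentage.

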#### 8.7 Protocol Deviations

Protocol deviations will be reviewed and assessed before database lock. The major protocol deviations are defined as those deviations from the protocol that are likely to have an impact on the subject's rights, safety, well-being, and/or on the validity of the data for analysis.

A summary of the number and percentage of patients with a major/minor protocol deviation as well as by type of deviation will be provided. Also, a by-subject listing of major/minor protocol deviations will be provided by treatment part, subject ID, and visit.

